8.3.6. Hypoglycemia

Participants will be trained by authorized study personnel about signs and symptoms of hypoglycemia and how to treat hypoglycemia. Hypoglycemia events entered into the participant e-diary will be available for review through a web-based portal that can be accessed by designated investigative site personnel at any time. CGM data will be available for site personnel to download and review through a web-based portal.

Hypoglycemia classification and definitions***Level 1***

Glucose <70 mg/dL (3.9 mmol/L) and \geq 54 mg/dL (3.0 mmol/L)

Level 1 hypoglycemia can alert a person to take action such as treatment with fast-acting carbohydrates. Providers should continue to counsel participants to treat hypoglycemia at this glucose alert value.

Level 2

Glucose <54 mg/dL (3.0 mmol/L)

Level 2 hypoglycemia is also referred to as documented or blood glucose-confirmed hypoglycemia. The glucose threshold is clinically relevant regardless of the presence or absence of symptoms of hypoglycemia.

Level 3 Severe

A severe hypoglycemic event is characterized by altered mental or physical status requiring assistance of another person to actively administer carbohydrate, glucagon, or other resuscitative actions for the treatment of hypoglycemia.

The determination of an episode of severe hypoglycemia is made by the investigator based on the medical need of the participant to have required assistance and is not predicated on the report of a participant simply having received assistance.

Examples of severe hypoglycemia in adults are

- altered mental status and the inability to assist in their own care
- semiconscious or unconscious, or
- coma with or without seizures.

Glucose measurements may not be available during such an event, but neurological recovery attributable to the restoration of glucose concentration to normal is considered sufficient evidence that the event was induced by a low glucose concentration.

Nocturnal hypoglycemia

Nocturnal hypoglycemia is a hypoglycemia event, including severe hypoglycemia, that occurs at night and presumably during sleep between midnight and 0600 (6:00 am).

Reporting of severe hypoglycemic events

If a hypoglycemic event meets the criteria of severe, the investigator must record the event as serious on the AE CRF and report it to Lilly as an SAE.

The investigator should also determine if repeated or prolonged episodes of hypoglycemia occurred prior to the severe event.

8.4. Pharmacokinetics

At the visits and times specified in the SoA, blood samples will be collected for all participants. Only samples from participants assigned to treatment with LY3209590 will be analyzed for drug concentration.

Instructions for the collection and handling of blood samples will be provided by the sponsor.

The actual date and time (24-hour clock time) of each sampling will be recorded.

Bioanalytical

Samples will be analyzed at a laboratory designated by the sponsor and stored at a facility designated by the sponsor. Concentrations of LY3209590 will be assayed using a validated bioanalytical method.

Sample retention is described in Section [10.1.12](#).

8.5. Pharmacodynamics

Pharmacodynamic parameters are described in Section [8.1](#).

8.6. Genetics

Genetics are not evaluated in this study.

8.7. Biomarkers

Serum and plasma samples will be used for exploratory biomarker research, where local regulations allow. See Clinical Laboratory Tests, and the SoA for sample collection information.

Samples will be used for research on the drug target, disease process, variable response to LY3209590 pathways associated with T1D, mechanisms of action of LY3209590 or research methods, or in validating diagnostic tools or assay(s) related to T1D.

Samples may be used for research to develop methods, assays, prognostics, and/or companion diagnostics related to the intervention target, disease state, pathways associated with disease, and/or the mechanism of action of the study intervention.

Sample retention is described in Section [10.1.12](#).

8.8. Immunogenicity Assessments

At the visits and times specified in the SoA (Section [1.3](#)), venous blood samples from all study participants will be collected for analysis to determine antibody production against LY3209590. Antibodies may be further characterized for cross-reactive binding to endogenous insulin.

To interpret the results of immunogenicity, a corresponding venous blood sample will be collected at the same visits to determine the concentrations of LY3209590 (PK sample). At Visit 3, the sample for immunogenicity should be taken before dosing and the PK sample for LY3209590 after dosing.

Instructions for the collection and handling of blood samples will be provided by the sponsor.

Treatment-emergent ADAs are defined in Section [9.3.6.2](#).

Immunogenicity will be assessed by a validated assay designed to detect and characterize ADA in the presence of LY3209590 at a laboratory approved by the sponsor.

Sample retention is described in Section [10.1.12](#).

8.9. Health Economics

Health economics parameters are not evaluated in this study.

9. Statistical Considerations

The first version of the SAP will be finalized prior to first participant visit, and it will include a more technical and detailed description of the statistical analyses described in this section. This section is a summary of the planned statistical analyses of the most important endpoints, including primary and key secondary endpoints.

9.1. Statistical Hypotheses

Primary hypothesis

The primary objective of this study is to test the hypothesis that LY3209590 is noninferior to insulin degludec on glycemic control as measured by change in HbA1c from baseline to Week 26 (Visit 22) in adults with T1D currently on basal-bolus insulin.

The null hypothesis (H_0) is the difference between LY3209590 and insulin degludec in the change in HbA1c from baseline to Week 26 (Visit 22) is greater than the NIM.

The NIMs of 0.4% and 0.3% will both be tested to meet different regulatory requirements. The 2-sided 95% CI will be used for testing the noninferiority.

Secondary hypotheses

The key secondary (multiplicity adjusted) objectives are to test the hypotheses that LY3209590 is superior to insulin degludec with respect to

- change in HbA1c from baseline to Week 26 (Visit 22)

H_0 : the difference (LY3209590 – insulin degludec) ≥ 0.0

- time in glucose range between 70 and 180 mg/dL (3.9 and 10.0 mmol/L) inclusive measured by CGM 4 weeks prior to Week 26 (Visit 22)

H_0 : the difference (LY3209590 – insulin degludec) ≤ 0.0

- the event rate of nocturnal hypoglycemia (<54 mg/dL [3.0 mmol/L] or severe) during treatment period up to Week 52 (Visit 29)

H_0 : the relative event rate (LY3209590 vs. insulin degludec) ≥ 1

These hypotheses and the primary hypothesis will be tested using a strategy to control the overall Type I error (see Section 9.1.1).

9.1.1. Multiplicity Adjustment

A graphical approach (Bretz et al. 2009, 2011) for multiple comparisons will be used to ensure the strong control of overall Type I error rate for testing the primary and key secondary (multiplicity adjusted) objectives.

The overall significance level (α) will be set to 0.05. The total α will be used for the primary objective first, then the α will be allocated and transitioned to key secondary objectives once the primary objective is met. The testing procedure and α allocation will be established according to the clinical importance and statistical power of the endpoints in this study population.

The details of graphical testing scheme will be described in the SAP.

9.2. Analyses Sets

For the purposes of analysis, this table defines the analysis sets for this study.

Analysis Populations/Sets	Description
Entered population	All participants who sign the informed consent form.
Randomized population	All randomized participants. Participants will be analyzed according to the treatment they were assigned.
Modified Intent-to-Treat (mITT) Population	All randomized participants who took at least 1 dose of LY3209590 or insulin degludec. Participants will be analyzed according to the treatment they were assigned.
Efficacy Analysis Set 1 (EAS1) for treatment regimen estimand	The data will include 
 • mITT Population excluding participants discontinuing the study treatment due to inadvertent enrollment • all measurements regardless of the use of study treatment or rescue medications
Efficacy Analysis Set 2 (EAS2) for efficacy estimand	The data will include 
 • mITT Population excluding participants discontinuing the study treatment due to inadvertent enrollment • measurement up to discontinuation of study treatment or the initiation of rescue medication
Safety Analysis Set (SS)	The data will include 
 • mITT Population • all measurements regardless of the use of study treatment or rescue medications

9.3. Statistical Analyses

9.3.1. General Considerations

Statistical analysis of this study will be the responsibility of Lilly or its designees.

Any change to the data analysis methods described in the protocol will require an amendment ONLY if it changes a principal feature of the protocol. Any other changes to the data analysis methods described in the protocol, and the justification for making the change, will be described in the SAP or the clinical study report. Additional exploratory analyses of data will be conducted as deemed appropriate.

Unless otherwise stated, the efficacy analyses will be conducted on either EAS1 or EAS2, and the safety analysis will be conducted on the SS. All tests of treatment effects using statistical models will be conducted at a 2-sided alpha level of 0.05 and 2-sided 95% CI will be provided.

Unless otherwise stated, the other secondary and tertiary efficacy measures will be analyzed on EAS2 using the data up to the discontinuation of LY3209590 or insulin degludec, defined by the date of last study dose +10 days or the initiation of rescue medication whichever is earlier.

Handling of missing, unused, and spurious data are addressed prospectively in the overall statistical methods described in the protocol and in the SAP, where appropriate. Adjustments to the planned analyses are described in the final CSR.

9.3.2. Primary Endpoint(s)/Estimand(s) Analysis

The primary objective is to compare the HbA1c change from baseline to Week 26 (Visit 22) between LY3209590 and insulin degludec and will be based on either of the 2 estimands

treatment regimen estimand for the US FDA submission, and

efficacy estimand for registrations in other countries as defined in Section 3 of this protocol.

Treatment regimen estimand

The treatment regimen estimand will be estimated using the HbA1c data at baseline and Week 26 (Visit 22) from the EAS1 regardless of the use of LY3209590 or insulin degludec or rescue medication.

Missing measures

The missing measures at the primary endpoint will be imputed using multiple imputation by the retrieved dropout approach. The retrieved dropout participants are those who discontinue LY3209590 or insulin degludec prior to Week 26 (Visit 22) but have non-missing measures at Week 26 (Visit 22).

If there are only a limited number of retrieved participants that leads to a failure in performing the multiple imputation analysis, such as the model cannot converge, or the number of retrieved dropout participants is small, the missing HbA1c at Week 26 (Visit 22) will be imputed by return-to-baseline multiple imputations.

Analysis model

After the imputation, the observed and imputed data will be analyzed by the ANCOVA.

The model will include treatment, strata (country, CGM use prior to study entry [yes/no], and carbohydrate counting for prandial insulin dosing [yes/no]), and baseline value of the dependent variable (HbA1c). The statistical inference will be based on the multiple imputation framework by Rubin (1987).

Efficacy estimand

The efficacy estimand is the treatment differences in the change in HbA1c from baseline to Week 26 (Visit 22) if all participants would adhere to the treatment without intercurrent events.

The HbA1c collected at all planned postbaseline visits from the EAS2 will be used in the analysis.

Missing measures

There may be missing values due to the early discontinuation of LY3209590 or insulin degludec or use of rescue medication. The MMRM model will be used, and the missing values will be handled implicitly in the MMRM analysis under the assumption of missing at random.

Analysis model

The MMRM model will include treatment, strata (country, CGM use prior to study entry [yes/no], and carbohydrate counting for prandial insulin dosing [yes/no]), visit and treatment-by-visit interaction as fixed effects, and baseline of the dependent variable (HbA1c) as a covariate.

The Kenward-Roger approximation will be used to estimate denominator degrees of freedom for the MMRM models. An unstructured covariance structure will be used to model the within-participant errors. If this structure fails to converge, the following covariance structures will be used in order until one converges:

1. Toeplitz with heterogeneity
2. autoregressive with heterogeneity
3. compound symmetry with heterogeneous variances
4. Toeplitz
5. autoregressive, and
6. compound symmetry without heterogeneous variances.

The 2-sided 95% CI of the LS mean for individual treatment groups and treatment LS mean difference for the HbA1c change from baseline to Week 26 (Visit 22) will be estimated. For both estimands, LY3209590 will be declared noninferior to insulin degludec if the upper limit of the 2-sided 95% CI for the LS mean difference in the HbA1c change from baseline is below NIM (+0.4% or +0.3% for different regulatory requirements).

The HbA1c is reported in % units and will be converted to mmol/mol using this formula.

$$\text{HbA1c in mmol/mol} = 10.93 \times \text{HbA1c in \%} - 23.5 \text{ (NGSP IFCC Standardization of HbA1c page [www.ngsp.org/ifccngsp.asp])}$$

9.3.3. Secondary Endpoints Analysis

9.3.3.1. Multiplicity Adjusted Endpoints

A graphical approach will be used to control the overall Type I error for the primary objective and testing the superiority of LY3209590 compared with insulin degludec for

- change in HbA1c from baseline to Week 26 (Visit 22)
- time in normal glucose range between 70 and 180 mg/dL (3.9 and 10.0 mmol/L) inclusive, measured by CGM 4 weeks prior to Week 26 (Visit 22), and
- event rate of participant-reported clinically significant nocturnal hypoglycemia (<54 mg/dL [3.0 mmol/L] or severe) during treatment phase up to Week 52 (Visit 29).

The superiority test in change from baseline to Week 26 (Visit 22) in HbA1c will be based on the same primary endpoint analysis methods as described above.

The rate of nocturnal hypoglycemia will be analyzed by a negative binomial regression with treatment, baseline HbA1c, baseline incidence of nocturnal hypoglycemia, and carbohydrate counting for prandial insulin dosing (yes/no) as independent variables, and log (exposure in year) as the offset.

The time in glucose range between 70 and 180 mg/dL (3.9 and 10.0 mmol/L) inclusive measured by CGM will be analyzed using an ANCOVA model for treatment regimen estimand (using data from EAS1) and an MMRM model for efficacy estimand (using data from EAS2).

In the ANCOVA model, treatment, strata (country, baseline HbA1c stratum [$<8.0\%$, $\geq 8.0\%$]), CGM use prior to study entry [yes/no], and carbohydrate counting for prandial insulin dosing [yes/no]), and baseline of the dependent variable will be used.

The MMRM model will include treatment, strata (country, baseline HbA1c stratum [$<8.0\%$, $\geq 8.0\%$]), CGM use prior to study entry [yes/no], and carbohydrate counting for prandial insulin dosing [yes/no]), visit and treatment-by-visit interaction as fixed effects, and baseline of the dependent variable as a covariate.

For treatment regimen estimand, the missing data will be imputed by multiple imputation with the approach similar to the imputation used for the primary endpoint.

9.3.3.2. Other Secondary Endpoints

Other secondary endpoints include various measures for efficacy, safety, and patient-reported outcome questionnaires.

Efficacy measures and patient-reported questionnaires will be analyzed using the EAS2 unless otherwise noted.

Safety measures will be analyzed using the SS regardless of LY3209590 or insulin degludec discontinuation and use of rescue medications.

Analysis details will be provided in the SAP.

9.3.4. Tertiary Endpoints Analysis

Refer to the SAP for analyses related to tertiary endpoints.

9.3.5. Safety Analyses

Safety measures include

- treatment exposure
- AE
- vital signs
- weight
- hypoglycemia
- laboratory measures and
- immunogenicity.

All safety analyses will be based on the SS.

Events that are newly reported after the first dose of LY3209590 or insulin degludec or reported to worsen in severity from baseline will be considered TEAEs. The Medical Dictionary for Regulatory Activities lowest level term will be used in the treatment-emergent assessment. The maximum severity for each lowest level term during the baseline period will be used as baseline severity.

Summary statistics will be provided for incidence of

- TEAEs
- SAEs

- study discontinuation due to AEs
- intervention discontinuation due to AEs, and
- deaths.

For continuous safety variables, such as laboratory measures, vital signs, and weight, the MMRM or ANCOVA models will be used.

For categorical safety variables, such as AEs, incidence of hypoglycemia, treatment-emergent abnormal laboratory measurements, either the Fisher's exact test or logistic regression will be used for treatment comparison.

Hypoglycemia analysis

The participant-reported hypoglycemia will be analyzed using data from the e-diary by

- Level 1 (defined by glucose value ≥ 54 to < 70 mg/dL [3.0 to 3.9 mmol/L])
- Level 2 (defined by glucose < 54 mg/dL [3.0 mmol/L])
- Level 3 (severe hypoglycemia), and
- the composite of Levels 2 and 3.

The analysis periods of 0 to 6, 0 to 12, 0 to 26, 0 to 52, 12 to 26, and 26 to 52 weeks of treatment will be considered. Documented hypoglycemia will be defined as

- All documented hypoglycemia - episodes for the 24-hour period
- Non-nocturnal hypoglycemia - episodes during 6 AM to midnight, and
- Nocturnal hypoglycemia - episodes during midnight to 6 AM.

The incidence and rate of hypoglycemia will be summarized by treatment and analysis period for different types of hypoglycemia.

Further details for assessing all safety measures will be described in the SAP.

9.3.6. Other Analyses

9.3.6.1. Pharmacokinetic and Pharmacodynamic Analyses

LY3209590 concentration data will be analyzed using a population PK approach via nonlinear mixed-effects modeling with the NONMEM software.

The relationships between LY3209590 dose and/or concentration and efficacy, and safety as well as biomarker endpoints may be characterized.

In addition, if population PK and PK/PD models can be established, the impact of additional participant factors, such as age, weight, sex, and renal function on PK and/or PD parameters, may be examined.

Should antidrug antibody be detected from immunogenicity testing, its impact on LY3209590 PK or any relevant PD parameters will also be examined.

9.3.6.2. Evaluation of Immunogenicity

The baseline anti-LY3209590-antibody (ADA) status (detected or not detected) will be summarized by treatment for the participants evaluable for TEADA defined as participants with non-missing baseline and at least 1 non-missing postbaseline measurement.

The number and percentage of participants who are TEADA+ will be summarized by treatment group.

The frequency of cross-reactive binding to endogenous insulins may also be summarized for the participants with TEADA+.

The relationship between the presence of TEADA and the safety and efficacy measures may be assessed.

Definition of TEADA+

A participant is considered TEADA+ if either treatment-induced ADA or treatment-boosted ADA occur.

Treatment-induced ADA is defined as the participant has baseline status of ADA Not Present and at least 1 postbaseline status of ADA Present with titer \geq 2-fold (1 dilution) of the minimum required dilution (1:20).

Treatment-boosted ADA is defined as the participant has baseline status of ADA Present and at least 1 postbaseline status of ADA Present with the titer being \geq 2 dilutions (4-fold) of the baseline titer. That is, the participant has baseline status of ADA Present, with titer 1:B, and at least 1 postbaseline status of ADA Present, with titer 1:P and P/B \geq 4.

9.4. Interim Analysis

A program-level safety review using selected efficacy and safety data will be conducted on a periodic basis across all ongoing Phase 3 clinical trials evaluating LY3209590. The analysis will be performed using the unblinded data and be reviewed by the DMC consisting of experienced members external to Lilly (Section 10.1.5).

Study team personnel will remain blinded. Detailed information for the data review and the unblinding are specified in the DMC Charter or a separate unblinding plan document.

9.5. Sample Size Determination

Approximately 670 participants will be randomized to LY3209590 and insulin degludec in a 1:1 ratio. With the assumption of 15% dropout at Week 26, approximately 284 and 284 participants will complete 26 weeks of treatment on LY3209590 and insulin degludec, respectively.

The primary objective of this study is to test the hypothesis that LY3209590 is noninferior to insulin degludec on glycemic control as measured by change from baseline to Visit 22 (Week 26) in HbA1c in participants with T1D currently basal-bolus insulin.

Assuming an NIM of 0.4%, no true difference between treatment groups, and an SD of 1.1%, 568 completers (284 on LY3209590 and 284 on insulin degludec) will provide at least 99% statistical power to show noninferiority between LY3209590 and insulin degludec using the upper limit of a 2-sided 95% CI (LY3209590 – insulin degludec). This sample size also has at least 90% statistical power to show noninferiority between LY3209590 and insulin degludec using a 0.3% NIM at Week 26.

The 568 completers will provide 90% statistical power to demonstrate the superiority (LY3209590 vs. insulin degludec) of change in HbA1c from baseline to 26 weeks (assuming an SD of 1.1% and true mean difference is -0.3%) using the alpha of 0.05.

The 568 completers will provide at least 99% statistical power to show the superiority of the percentage of time in glucose range between 70 and 180 mg/dL (3.9 and 10.0 mmol/L) inclusive measured by CGM 4 weeks prior to Week 26 between LY3209590 and insulin degludec (assuming an SD of 10% and true mean difference is 5%) at alpha = 0.05.

The 568 completers will provide 80% statistical power to show the superiority of the event rate of clinically significant nocturnal hypoglycemia (<54 mg/dL [3.0 mmol/L] or severe) during treatment phase up to Week 52 (assuming event rate of 3.37 [SD = 7.13] and 4.87 [SD = 7.13] events per participant per year for LY3209590 and insulin degludec, respectively) using a negative binomial distribution at alpha = 0.05.

10. Supporting Documentation and Operational Considerations

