Population-level summary	Difference in mean changes between treatment conditions.
--------------------------	--

Rationale for the treatment regimen estimand

The treatment regimen estimand estimates how participants with T1D are treated in clinical practice and considers both efficacy and safety.

Registration for countries outside the United States

The primary clinical question of interest is

What is the treatment difference between LY3209590 and insulin degludec in HbA1c change from baseline after 26 weeks of treatment, in study eligible participants with T1D treated with MDI therapy and adhere to the randomized treatment without an intercurrent event during the study treatment period?

Efficacy estimand attributes

This table describes the efficacy estimand attributes.

Efficacy Regimen Estimand Attribute	Description
Population	Targeted study population. (see table in Section 9.2).
Endpoint	HbA1c change from baseline to Week 26.
Remaining intercurrent events	None. The 2 intercurrent events, treatment discontinuation for any reason and initiation of rescue medication, are both addressed by the hypothetical strategy, for example, the potential outcome for those participants if the intercurrent events have not occurred will be estimated.
Treatment condition	The randomized treatment.
Population-level summary	Difference in mean changes between treatment conditions.

Rationale for the efficacy estimand

The efficacy estimand supports the interpretation of the treatment effect as participants adhere to study treatment and free from the confounding effect of rescue medications.

Secondary estimands for multiplicity-adjusted objectives

The superiority test in change from baseline to Week 26 (Visit 22) in HbA1c will also be based on the primary estimand described above.

The time in glucose range between 70 and 180 mg/dL (3.9 and 10.0 mmol/L), inclusive, measured by CGM in the 4 weeks prior to Visit 22 (Week 26) will use treatment regimen estimated for US registration and efficacy estimand for other countries.

The participant-reported clinically significant nocturnal hypoglycemia (<54 mg/dL [3.0 mmol/L] or severe) is one of the safety measures for the study. The event rate will be based on all available data during the specific analysis period. Relative rate between randomized treatment groups will be used for treatment comparison.

4. Study Design

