2.1. Multiplicity Adjustment

A graphical approach (Bretz et al. 2009, 2011) for multiple comparisons will be used to ensure the strong control of the overall type 1 error rate for testing the primary and key secondary (multiplicity adjusted) objectives. The overall significance level (α) will be set to 0.05. The total α will be used for the primary objective first, then the α will be allocated and transitioned to other key secondary objectives once the primary objective is met. Therefore, the noninferiority test for the primary objective will be based on the 2-sided 95% CI. Once the upper limit of the 2-sided 95% CI is below the NIM, the noninferiority will be achieved, and the α of 0.05 will be distributed to test superiority for the key secondary objectives. If the p-value of the 2-sided test for one of the key secondary objectives is below the assigned α level, the superiority is demonstrated, and the assigned α level will be distributed to the remaining objectives. The iterative test procedure continues until none of the remaining objectives can be demonstrated with their preserved α or all objectives are demonstrated successful. The NIM of 0.4% (for the treatment regimen estimand) and 0.3% (for the efficacy estimand) will both be tested to meet different regulatory requirements. No multiplicity adjustments will be made for conducting separate analyses relative to the efficacy and treatment regimen estimands. Each estimand will have its own familywise error rate of 0.05.

For primary and key secondary efficacy objectives, the details of the type 1 error control strategy are illustrated in [Figure BDCY.2.1](#). No multiplicity adjustments will be made for evaluating other secondary and exploratory objectives, or for safety assessments.

[figure not shown]

Figure BDCY.2.1. Type 1 error control strategy for primary and key secondary efficacy endpoints.

3. Analysis Sets

The following analysis populations and datasets are defined for the purpose of analysis.

Analysis Populations/ Datasets	Description
Entered Population	All participants who sign the informed consent form.
Randomized Population	All randomized participants. Participants will be analyzed according to the treatment they were assigned.
Modified Intent-to-Treat (mITT) Population	All randomized participants who took at least 1 dose of LY3209590 or insulin degludec. Participants will be analyzed according to the treatment they were assigned.

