4.9. Changes to Protocol-Planned Analyses

There are no changes but additional details are provided to the analyses described in the protocol.

5. Sample Size Determination

Approximately 670 participants will be randomized to LY3209590 and insulin degludec in a 1:1 ratio. With the assumption of 15% dropout at Week 26, approximately 284 and 284 participants will complete 26 weeks of treatment on LY3209590 and insulin degludec, respectively.

The primary objective of this study is to test the hypothesis that LY3209590 is noninferior to insulin degludec on glycemic control as measured by change from baseline to Visit 22 (Week 26) in HbA1c in participants with T1D currently basal-bolus insulin.

Assuming an NIM of 0.4%, no true difference between treatment groups, and an SD of 1.1%, 568 completers (284 on LY3209590 and 284 on insulin degludec) will provide at least 99% statistical power to show noninferiority between LY3209590 and insulin degludec using the upper limit of a 2-sided 95% CI (LY3209590 - insulin degludec). This sample size also has at least 90% statistical power to show noninferiority between LY3209590 and insulin degludec using a 0.3% NIM at Week 26.

The 568 completers will provide 90% statistical power to demonstrate the superiority (LY3209590 vs insulin degludec) of change in HbA1c from baseline to 26 weeks (assuming an SD of 1.1% and true mean difference of -0.3%) using the α of 0.05.

The 568 completers will provide at least 99% statistical power to show the superiority of the percentage of time in glucose range between 70 and 180 mg/dL (3.9 and 10.0 mmol/L), inclusive, measured by CGM 4 weeks prior to Week 26 between LY3209590 and insulin degludec (assuming an SD of 10% and true mean difference of 5%) using the α of 0.05.

The 568 completers will provide 80% statistical power to show the superiority of the event rate of clinically significant nocturnal hypoglycemia (<54 mg/dL [3.0 mmol/L] or severe) during the treatment phase up to Week 52 (assuming event rates of 3.37 [SD = 7.13] and 4.87 [SD = 7.13] events per participant per year for LY3209590 and insulin degludec, respectively) using a negative binomial distribution α of 0.05.

6. Supporting Documentation

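### The stated 80% power for nocturnal hypoglycemia with 568 completers does not follow from the stated inputs; under the plan's 2-sided 0.05 rule it is about 70% (67–73%)

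*Protocol*

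**What the plan says.** Protocol Section 9.5 and SAP Section 5 make the same claim: "The 568 completers will provide 80% statistical power to show the superiority of the event rate of clinically significant nocturnal hypoglycemia". The SAP gives the inputs as "assuming event rates of 3.37 [SD = 7.13] and 4.87 [SD = 7.13] events per participant per year", lower for LY3209590 and higher for insulin degludec. Both documents name a negative binomial distribution, alpha 0.05 and the treatment phase to Week 52. The completers are "568 completers (284 on LY3209590 and 284 on insulin degludec", and they are defined by Week 26: "With the assumption of 15% dropout at Week 26, approximately 284 and 284 participants will complete 26 weeks of treatment".

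The power sentence does not give sidedness, but other sections do. Protocol Section 9.3.1: "All tests of treatment effects using statistical models will be conducted at a 2-sided alpha level of 0.05". SAP Section 2.1 declares superiority on this basis: "If the p-value of the 2-sided test for one of the key secondary objectives is below the assigned α level".

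The planned analysis (Protocol Section 9.3.3.1, SAP Section 4.6.3.1.1) is a negative binomial regression with covariates and a log-exposure offset. Protocol Section 3 adds: "The event rate will be based on all available data during the specific analysis period".

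**The concern.** The power sentence contains everything needed to recompute it except sidedness, and the general rules supply that. A plain calculation lands well below 80%, while the other power figures in the same section come out as stated.

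Nocturnal hypoglycemia is one of three key secondary superiority claims under type 1 error control. If its power at the assumed effect is nearer 70%, a non-significant result is weaker evidence against that effect than a reader would infer from 80%. A reader also cannot tell which sidedness, sample size, exposure or dispersion produced the figure.

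**Working it through.** **Inputs** (Protocol 9.5, SAP 5): n = 284 per arm; μ1 = 3.37, μ0 = 4.87; SD = 7.13 in each arm. Sidedness: 2-sided 0.05, critical value 1.96 (Protocol 9.3.1, SAP 2.1). Assumption: one year of exposure per participant, because the rates are annual and the endpoint runs to Week 52.

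**Check of the method on the same section.** The protocol says: "The 568 completers will provide 90% statistical power to demonstrate the superiority (LY3209590 vs. insulin degludec) of change in HbA1c", with a difference of −0.3 and SD 1.1.
- SE = 1.1 × √(2/284) = 0.0923, and 0.3/0.0923 = 3.25.
- 2-sided: Φ(3.25 − 1.96) = 90.1%. 1-sided: Φ(3.25 − 1.645) = 94.6%.
- The stated 90% is therefore the 2-sided figure. Noninferiority also reproduces: 99.1% at the 0.4 margin and 90.1% at 0.3.

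**Dispersion implied by the stated SDs.** Negative binomial variance is μ + kμ², so k = (SD² − μ)/μ², with SD² = 50.84.
- LY3209590: (50.84 − 3.37)/3.37² = 4.18.
- Degludec: (50.84 − 4.87)/4.87² = 1.94.
- Common k at the mean rate 4.12: (50.84 − 4.12)/4.12² = 2.75.
- Common k pooled as Σ(SD² − μ)/Σμ²: 93.43/35.07 = 2.66.

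**Power.** The log rate ratio is ln(3.37/4.87) = −0.368. Its SE is √{[1/3.37 + k1 + 1/4.87 + k0]/n}, and power is Φ(0.368/SE − z). For the means, power is Φ(1.50/(7.13 × √(2/n)) − z).

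| Approach | SE of log rate ratio, n = 284 | n = 284, 2-sided | n = 284, 1-sided 0.05 | n = 335, 2-sided |
|---|---|---|---|---|
| Arm-specific k | 0.153 | 67.4% | 77.8% | 74.5% |
| Difference in means | – | 70.8% | 80.6% | 77.7% |
| Common k 2.75 | 0.145 | 71.6% | 81.2% | 78.5% |
| Common k 2.66 | 0.143 | 72.9% | 82.2% | 79.7% |

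**Simulation** (common-k negative binomial fit, Wald test, 284 per arm, 2-sided): 70.6% (4,000 trials) and 71.9% (5,000 trials) with counts generated from the arm-specific k, and 72.2% with counts from k = 2.75. The 1-sided figures are 80.3%, 80.9% and 81.5%. A variant that uses the null variance in the closed form reaches 73.6%.

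**What would give 80%.**
- A 1-sided 0.05 test with 284 per arm: 78–82%. This contradicts the 2-sided rule.
- All 335 per arm followed for a full year, 2-sided: 74.5–80%. This contradicts the reference to 568 completers.
- A common k of 2.20 with 284 per arm, 2-sided. This implies one-year SDs of √(3.37 + 2.20 × 3.37²) = 5.33 and √(4.87 + 2.20 × 4.87²) = 7.56, not 7.13 in either arm.
- One arm's k used in both arms does not give 80%: 84.3% with 1.94, 55.0% with 4.18.

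**The case against.** **The SD may not be a one-year SD.** The documents do not say over what follow-up 7.13 was observed. If it is the SD of annualized rates from a shorter period t, then k = (SD² − μ/t)/μ² is smaller and power is higher. At t = 0.5 the three negative binomial figures become 70.8%, 75.2% and 76.4%. At about 16 weeks (t ≈ 0.3) they are about 76%, 80% and 81%. The arithmetic is right, but nothing in either document points to a 16-week source, and a 26-week source still falls short. It is a further reason to state the basis of the SD.

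**The planned test is stronger than the calculation.** It uses all dosed participants, an exposure offset and covariates. This stands in part.
- Adding 51 non-completers per arm (335 − 284) with 0.1 to 0.5 year each (assumption), each contributing information μt/(1 + kμt), gives 71.8–74.1% with arm-specific k and 75.8–79.2% with a common k.
- If covariates removed 20% of the dispersion (assumption), 284 per arm gives 76.1% with arm-specific k, and 80.0% or 81.1% with common k of 2.75 or 2.66.

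So the shortfall of the test actually run may be smaller than the sentence's own shortfall. But neither document invokes these gains, and the sentence credits the 80% to the 568 completers.

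**Week 26 against Week 52.** This matters little numerically. A further 5–10% loss after Week 26, at 0.75 year each (assumption), lowers power by under 0.2 points. It is a point of clarity only.

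**Alpha.** The figure showing how alpha is passed among the key secondary tests is not available here. Every figure above uses the full 0.05, as the power sentence does. Any split would lower power.

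**Conclusion.** The stated 80% is wrong as written. With the documents' own inputs, 284 per arm, one year of exposure and a 2-sided 0.05 test, power is about 70% (67–73%), which is 7 to 13 points below the claim. The corresponding chance of missing the assumed effect is 27–33%. This rests on reading SD 7.13 as a one-year SD and on no gain from covariates or from partial exposure of non-completers; those could bring the planned test closer to 80%. The documents do not show whether a 1-sided alpha, the full 670 or some other dispersion lies behind the figure. The primary noninferiority power is not affected.

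**What to change.** In Protocol Section 9.5 and SAP Section 5, do one of two things:

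- restate the power for this endpoint as about 70% (67–73%) for 568 completers at 2-sided alpha 0.05; or
- give the sidedness, N, exposure per participant and dispersion (with the follow-up on which SD 7.13 is based) that yield the stated figure under the 2-sided test.

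In either case, say that the 568 are Week 26 completers and what exposure to Week 52 is assumed.

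The cost is one sentence in each document. The test, estimand and enrolment stay as they are; the quoted power may become less favourable.
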